3.5.4. REPORTING OF ADVERSE EVENTS

AEs reporting, including SUSARs, will be carried out in accordance with applicable local regulations. For reported deaths, the Investigator should supply the Sponsor and the

IEC/IRB with any additional requested information (e.g., autopsy reports and terminal medical reports).

After termination of the clinical study (last subject last visit in the study), any unexpected safety issue that changes the risks benefit analysis and is likely to have an impact on the subjects who have participated in it, will be reported by the Sponsor as soon as possible to the competent authority(ies) concerned together with proposed actions.

3.5.5. FOLLOW-UP OF ADVERSE EVENTS

AEs will be handled according to common clinical practice. If necessary, in order to obtain additional information to ensure safety to the subject, additional blood and urine samples may be taken at the discretion of the Investigator. Information relative to other means of investigational diagnostics used in relation to the AE will also be communicated.

AEs are recorded from signing the ICF until completion of the subject's last visit.

All AEs occurring at any time during the study (including the follow-up period) will be followed until satisfactory outcome.

3.5.6. OTHER REPORTABLE INFORMATION

3.5.6.1. PREGNANCY

The Investigator must report to the Sponsor any pregnancy occurring in a study subject, or in his partner, during the subject's participation in this study and until 3 months after last study drug dose. The report should be submitted within the same timelines as an SAE, although a pregnancy per se is not considered an SAE.

For a study subject, the outcome of the pregnancy should be followed up carefully, and any abnormal outcome of the mother or the child (e.g., stillbirth, spontaneous abortion or elective abortion) should be reported.

For the pregnancy of a study subject's partner, all efforts should be made to obtain similar information on course and outcome.

All pregnancies including study subjects and female partners should be reported using the pregnancy form.

Note that as indicated in section [3.2.3.2](#), subjects who get pregnant during the study should be withdrawn from the study.

3.5.6.2. MEDICATION ERROR

Medication errors include, but are not limited to, the following:

- Administration of the wrong dosage (including overdose) to the subject.
- Administration of the study drug that has not been assigned to the subject.
- Administration of expired study drug.
- Administration by a route (e.g., i.m.) other than s.c.
- Deviations to the study drug storage conditions only when administered to the subject.

Medications errors with signs and symptoms need to be reported as an AE/SAE.

Medication errors that occur during the study should be documented and reported to the Sponsor or designee whether or not it results in an AE/SAE.

3.6. STATISTICS

3.6.1. STUDY POPULATIONS

The following populations will be considered for analysis:

- **Modified Intent-to-treat (mITT) Population:** All randomized subjects who received at least 1 administration of study drug, as randomized.
- **Safety Population:** All subjects who received at least 1 administration of study drug, as treated.
- **PK Population:** Consists of a subset of the safety population, for whom the primary PK data are considered to be sufficient and interpretable.
- **Per Protocol (PP) Population:** Consists of a subset of the mITT population, and excludes those subjects who have had a major protocol violation or deviation. All violations and deviations will be reviewed prior to database lock and classified as major or minor.

Unless otherwise specified, the mITT Population will be used for the analysis of efficacy, the safety population for analysis of safety, PD, and immunogenicity data, while the PK population will be used for analysis of the PK variables.

3.6.2. STATISTICAL AND ANALYTICAL PLAN

The SAP, will be generated under responsibility of the Sponsor. The SAP will be finalized prior to database lock. Any deviation from the reporting and analysis plan will be reported in the section "Changes in the planned analysis" in the Clinical Study Report.

Details of the data analyses will be specified in the SAP.

3.6.3. DETERMINATION OF SAMPLE SIZE

Up to approximately 300 subjects will be randomized over 5 treatment arms in a 1:1:1:1:1 ratio. Randomization will be stratified by geographic region.

Simulations were performed to evaluate the power of detecting a significant dose-response relationship, i.e., whether changes in ALX-0061 dose regimen lead to significant changes in mBICLA response rate at Week 24 by using the MCP-Mod methodology [1]. A set of 5 plausible candidate models containing both monotonous and non-monotonous exposure-response shapes was defined. For these models an estimated placebo response rate of 25%, and a difference in response rate between the ALX-0061 dose regimen with the largest response rate and placebo of 25% was assumed, taking into account a discontinuation rate of 15% (homogeneous over treatment arms). With this methodology a

sample size of 60 subjects per arm will provide at least 85% power at a family-wise 5% significance level.

3.6.4. INITIAL CHARACTERISTICS OF SUBJECT SAMPLE

The statistical evaluation will be descriptive and by treatment (including mean, standard deviation, median, maximum, and minimum) for continuous variables and counts and percentages for categorical variables.

3.6.5. EVALUATION OF EFFICACY PARAMETERS

The adjudication committee will also evaluate appropriateness of data for evaluating the primary endpoint.

The primary endpoint is the percentage of subjects who achieved a response at Week 24 according to the composite mBICLA (BILAG-based Combined Lupus Assessment) score. BICLA responders are defined as subjects who meet all of the following criteria:

- (1) BILAG-2004 improvement: all A scores at baseline improved to B/C/D, and all B scores improved to C or D.
- (2) no worsening in disease activity: no new BILAG-2004 A scores and ≤ 1 new B score.
- (3) no worsening of total mSLEDAI-2K score from baseline.
- (4) no significant deterioration ($< 10\%$ worsening) in PGA.
- (5) no treatment failure (i.e., new or increased immunosuppressives or anti-malarials; or non-protocol allowed increased oral or parenteral corticosteroids; or premature discontinuation from study treatment).

The following efficacy analyses will be performed in addition to the primary analysis:

- Composite endpoint (m)BICLA over time (through Week 48) will be summarized by treatment group.
- Composite endpoint mSRI as well as standard SRI over time (through Week 48) will be summarized by treatment group.
- (m)SRI with more stringent (m)SLEDAI-cut-offs: SRI-5, SRI-6, SRI-7, SRI-8 over time (through Week 48) will be summarized by treatment group.
- Change from baseline in mSLEDAI-2K total score as well as standard SLEDAI-2K measured over time (through Week 48) will be summarized by treatment group.
- Number and percent of subjects with BILAG-2004 improvement.
- BILAG-2004 (total score) over time (through Week 48) will be summarized by treatment group.
- Improvement in individual organ systems of the BILAG-2004 over time (through Week 48) will be summarized by treatment group.

- Number of BILAG-2004 systems in which activity increased, decreased or remained the same compared to previous visit (BILAG-2004 systems tally) over time (through Week 48) will be summarized by treatment group.
- Change from baseline in PGA over time (through Week 48) will be summarized by treatment group.
- Change from baseline in patient's global assessment over time (through Week 48) will be summarized by treatment group.
- Change from baseline in proteinuria/urine sediment/serum creatinine/eGFR over time (through Week 48) will be summarized by treatment group.
- Proportion of treatment failures (defined as non-protocol allowed increase in steroid dose, start i.v. or i.m. steroids, start or increase of immunosuppressant) at Week 24 and at Week 48 will be summarized by treatment group.
- Reduction in flare rate at Week 24 and at Week 48.
 - Severe flare defined as a new A score in any system of the BILAG-2004 index; moderate flare defined as a new B score following a C, D or E score.
 - SFI.
- Percent change from baseline in daily dose of steroids at Week 24 and 48 will be summarized by treatment group.
- Percent subjects whose prednisone equivalent dose was >7.5 mg/day at baseline and reduced to ≤ 7.5 mg/day during Weeks 40–48 without experiencing a flare will be summarized by treatment group.
- Percent subjects who are able to discontinue prednisone by Week 48 without experiencing a flare will be summarized by treatment group.
- Changes from baseline in the physical and mental component scores of SF-36 at Week 24 and at Week 48 will be summarized by treatment group.
- 28 Joints count over time and change from baseline in 28 joint count over time will be summarized by treatment group.
- CLASI over time and change from baseline evaluation at Week 12, 24 and Week 48 will be summarized by treatment group.
- PK parameters.
- PD markers, including total sIL-6R, CRP, fibrinogen, anti-dsDNA, C3, C4, CH50.

Descriptive subgroup analyses may be performed to evaluate consistency of the primary endpoint over covariates including demographics (including weight and region), baseline disease, and prior and concomitant medications. Details will be provided in the SAP.

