Secondary endpoints will include:

- Composite endpoint (m)BICLA over time.
- Composite endpoint mSRI as well as standard SRI over time.
- (m)SRI with more stringent (m)SLEDAI-cut-offs: SRI-5, SRI-6, SRI-7, SRI-8 over time.
- Change from baseline in mSLEDAI-2K total score as well as standard SLEDAI-2K measured over time.
- Number and percent of subjects with BILAG-2004 improvement.
- BILAG-2004 (total score) over time.
- Improvement in individual organ systems of the BILAG-2004 over time.
- Number of BILAG-2004 systems in which activity increased, decreased or remained the same compared to previous visit (BILAG-2004 systems tally) over time.
- Change from baseline in PGA over time.
- Change from baseline in patient's global assessment over time.
- Change from baseline in proteinuria/urine sediment/serum creatinine/eGFR over time.
- Proportion of treatment failures (defined as non-protocol allowed increase in steroid dose, start i.v. or i.m. steroids, start or increase of immunosuppressant) at Week 24 and at Week 48.

- Reduction in flare rate at Week 24 and at Week 48.
 - Severe flare defined as a new A score in any system of the BILAG-2004 index; moderate flare defined as a new B score following a C, D or E score.
 - SLEDAI flare index (SFI).
- Percent change from baseline in daily dose of steroids at Week 24 and 48.
- Percent subjects whose prednisone equivalent dose was >7.5 mg/day at baseline and reduced to ≤7.5 mg/day during Weeks 40–48 without experiencing a flare.
- Percent subjects who are able to discontinue prednisone by Week 48 without experiencing a flare.
- Changes from baseline in the physical and mental component scores of SF-36 at Week 24 and at Week 48.
- 28 Joints count over time and change from baseline in 28 joint count over time.
- Cutaneous lupus erythematosus disease area and severity index (CLASI) over time and change from baseline evaluation at Week 12, 24 and Week 48.
- PK parameters.
- PD markers, including total sIL-6R, CRP, fibrinogen, anti-dsDNA, C3, C4, CH50.

Pharmacokinetics

Samples for determination of ALX-0061 serum levels.

Pharmacodynamics

Samples for determination of biomarker levels, including but not limited to total sIL-6R, CRP, fibrinogen, anti-dsDNA, C3, C4, CH50.

Samples for determination of additional biomarker levels (exploratory), including but not limited to uMCP-1, plasma cells, T helper 17 (Th17) and regulatory T (Treg) cells.

Immunogenicity

Samples for determination of anti-ALX-0061 antibodies.

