3.2.1. INCLUSION CRITERIA

Each subject must satisfy the following criteria at screening and baseline to be enrolled in the study:

1. Male or female adults ≥ 18 years and < 65 years of age at the time of signing the informed consent form (ICF). The minimum age for adults will depend on local regulations.
2. Have a diagnosis of SLE for at least 6 months prior to screening and fulfill the 1997 ACR (see Appendix 9.1) or 2012 Systemic Lupus International Collaborating Clinics (SLICC) classification criteria (see Appendix 9.2).
3. Have moderate to severe active SLE, for the purpose of this study defined by a SLEDAI-2K score ≥ 6 at screening.
4. Have at least one A or one B score on the revised BILAG-2004 criteria for the mucocutaneous and/or musculoskeletal system.
5. Have seropositive disease at screening for ANA ($\geq 1:80$) and/or anti-dsDNA (value above upper limit of laboratory normal range as measured by Farr assay) measured at the central laboratory.
6. Subject at least must be on one or more of the following treatments for SLE:
 - a. If subject is on oral corticosteroids, the dose should be equivalent to a maximum dose of 25 mg of prednisone/day and stable for at least 4 weeks prior to baseline.
 - b. If subject is on antimalarials, he or she must have received antimalarials for at least 12 weeks with a stable dose of max. 400 mg/day for at least 4 weeks prior to baseline.
 - c. If subject is on immunosuppressants: azathioprine (max. 150 mg/day), mycophenolate mofetil (max. 2.0 g/day), methotrexate (max. 25 mg/week), cyclosporine (max. 200 mg/day), leflunomide (max. 20 mg/day), treatment duration must be at least 12 weeks with a stable dose for at least 4 weeks prior to baseline; either alone or in combination with corticosteroids and/or hydroxychloroquine.
7. If immunosuppressants were previously given but have been stopped, the last dose should have been received more than 4 weeks prior to baseline; for leflunomide and hydroxychloroquine, a leflunomide or hydroxychloroquine treatment-free period of at least 12 weeks should be respected (unless an adequate cholestyramine wash-out was done for leflunomide).
8. If subject is on angiotensin-converting-enzyme (ACE) inhibitor or angiotensin receptor blocker, the dose should have been stable for 4 weeks prior to baseline.

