3.4.3.2. SYSTEMIC LUPUS ERYTHEMATOSUS DISEASE ACTIVITY INDEX 2000

The clinical SLEDAI-2K [40] assessments will be performed by the Investigator and the laboratory assessments will be performed by the central laboratory at visits as indicated in the [Schedule of Assessments](#).

The same trained and qualified physician should preferably be performing the assessment at each visit for each subject.

A process to check eligibility will also be installed centrally as well as central adjudication of SLEDAI-2K at baseline, Week 24 and Week 48.

The SLEDAI-2K is a one-page weighted scale for 24 items (seizure, psychosis, organic brain syndrome, visual disturbance, cranial nerve disorder, lupus headache, cerebrovascular accident, vasculitis, arthritis, myositis, urinary casts, hematuria, proteinuria, pyuria, rash, alopecia, mucosal ulcers, pleurisy, pericarditis, low complement, increased DNA binding, fever, thrombocytopenia, leukopenia). The manifestations felt to be most commonly contributing to disease activity are included and scored based on the presence or absence within 30 days prior to the evaluation. The total score can range from 0-105 and reflects all aspects of disease activity.

A modified SLEDAI-2K index (mSLEDAI-2K) will be derived from the standard index by omitting 1 of the standard items (low complement). An anti-IL-6R compound strongly decreases production of acute phase reactants, including complement [24, 25]. Therefore, the complement (C3/C4) values (parameters of the low complement item in the SLEDAI-2K index) may be decreased due to decreased production while effect on complement consumption (relevant for disease activity evaluation) cannot be assessed.

The SLEDAI-2K (both the standard and modified [excluding the low component item] version) score will be evaluated as an individual item as well as a component of the composite mBICLA score, composite mSRI index and SLEDAI flare index (SFI) index. Note that the mBICLA score and mSRI index uses the mSLEDAI-2K score only.

The SLEDAI-2K scoring table is provided in Appendix 9.7.

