3.4.3.7. SYSTEMIC LUPUS ERYTHEMATOSUS RESPONDER INDEX (SRI)

The composite index SRI enables quantification of decrease and increase in disease activity in a broad spectrum of manifestations thereby offering a comprehensive assessment of SLE disease status [41].

SRI combines advantages from three validated measurement tools:

- SLEDAI covers global disease improvement,
- BILAG covers organ specific disease worsening or improvement and
- PGA is used as a validity and safety net for items that were not addressed by the other two indices.

The composite SRI criteria for response are:

- SLEDAI-2K: ≥ 4 point reduction.
- BILAG: no new A domain score and no more than 1 new B domain score.
- PGA: no worsening (<10% increase).

When all three criteria are met, the subject is a responder according to the SRI at that time point, i.e., a clinically meaningful improvement of disease is detected.

In addition the modified SRI (mSRI) will be assessed, i.e., using the modified (excluding the low component item) version of the SLEDAI-2K as a criterion.

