3.6.5.2. SECONDARY EFFICACY ENDPOINTS

All secondary efficacy endpoints will be summarized by treatment group, using the observed data in the mITT population. For continuous secondary efficacy endpoints, summary statistics include mean, standard deviation, median, minimum and maximum, while for categorical secondary efficacy endpoints frequencies and proportions are provided.

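### Does summarising (m)SRI-5 to (m)SRI-8 over the whole mITT population misstate response, when some subjects start too low to reach the cut-off?

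*Protocol*

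**What the plan says.** Five parts of the protocol bear on the point.

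- **Entry.** Inclusion criterion 3 (section 3.2.1) requires active disease, "for the purpose of this study defined by a SLEDAI-2K score ≥ 6 at screening". This is the standard index. In Appendix 9.7 the low-complement item carries 2 points of it.
- **Modified index.** Section 3.4.3.2: "A modified SLEDAI-2K index (mSLEDAI-2K) will be derived from the standard index by omitting 1 of the standard items (low complement"). The stated reason is that an anti-IL-6R compound lowers complement production, so the item may no longer reflect disease activity.
- **Response rule.** Section 3.4.3.7 sets "SLEDAI-2K: ≥ 4 point reduction" as the index criterion for SRI, to be met together with the BILAG and PGA criteria. mSRI applies the same rule to mSLEDAI-2K.
- **Stricter versions.** The synopsis lists "m)SRI with more stringent (m)SLEDAI-cut-offs: SRI-5, SRI-6, SRI-7, SRI-8 over time" among the secondary endpoints, and section 3.6.5 repeats the item as a summary by treatment group: "m)SRI with more stringent (m)SLEDAI-cut-offs: SRI-5, SRI-6, SRI-7, SRI-8 over time (through Week 48) will be summarized by treatment group".
- **Population.** Section 3.6.5.2 summarises all secondary efficacy endpoints "using the observed data in the mITT population". Section 3.6.1 defines that population as "All randomized subjects who received at least 1 administration of study drug, as randomized", with no condition on the baseline score.

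Section 3.6.2 leaves details of the analyses to the SAP, which is not among the documents at hand.

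**The concern.** SLEDAI-2K cannot go below 0, so the largest possible fall equals the baseline score. A subject who enters at 6 can never show a fall of 7 or 8. If 2 of the 6 points are low complement, mSLEDAI-2K starts at 4 and even a 5-point fall is impossible. Such subjects stay in the mITT denominator and can never enter the numerator.

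This looks like a mismatch between the entry criterion and the endpoint. The rates at the strict cut-offs, and the absolute differences between arms, would be pulled towards zero by subjects who had no chance to respond. In a dose-finding study, a reader of a low SRI-8 rate could not tell from that table alone whether the drug did little or few subjects had enough activity to lose. The share affected also differs between SRI-k and mSRI-k at the same k, because of the low-complement item.

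**Working it through.** **1. The scale.** Section 3.4.3.2 gives a range of 0 to 105. The weights in Appendix 9.7 reproduce it: 8×8 + 6×4 + 7×2 + 3×1 = 64 + 24 + 14 + 3 = 105. Without low complement the maximum is 103. The floor is 0 on both versions.

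**2. Who cannot reach which cut-off.** SRI-k needs baseline S ≥ k. mSRI-k needs S − 2 ≥ k if low complement is scored, otherwise S ≥ k.

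| Baseline SLEDAI-2K | SRI out of reach | mSRI out of reach, low complement scored | Strict endpoints lost of 8, without / with low complement |
|---|---|---|---|
| 6 | 7, 8 | 5, 6, 7, 8 | 4 / 6 |
| 7 | 8 | 6, 7, 8 | 2 / 4 |
| 8 | none | 7, 8 | 0 / 2 |
| 9 | none | 8 | 0 / 1 |
| 10 | none | none | 0 / 0 |

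Such subjects can enrol: rash 2, increased DNA binding 2 and low complement 2 add up to 6. Criterion 3 names screening only, although the heading of the criteria list says screening and baseline. If a baseline score below 6 can occur, more subjects are affected.

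**3. Effect on the mITT table.** If a share f cannot respond, the rate in each arm is (1 − f) times the rate among those who can. The difference shrinks by the same factor and the ratio does not change. The protocol does not give f, so f = 10%, 30% and 50% are assumptions, as are rates of 30% and 50% among subjects able to respond. The number observed per arm is taken as 60 × 0.85 = 51. This applies the planning figure in section 3.6.3 ("taking into account a discontinuation rate of 15% (homogeneous over treatment arms")) to the visit, which is a further assumption.

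mITT: half-width = 1.96 × √[(p₁(1 − p₁) + p₂(1 − p₂))/51].

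Restricted to subjects able to respond: n = 51(1 − f) and half-width = 1.96 × √[(0.30×0.70 + 0.50×0.50)/n] = 1.96 × √(0.46/n).

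| f | mITT rates | mITT difference (half-width), points | Difference/SE | Restricted n per arm | Restricted difference (half-width), points | Difference/SE |
|---|---|---|---|---|---|---|
| 10% | 27% v 45% | 18 (18.3) | 1.93 | 45.9 | 20 (19.6) | 2.00 |
| 30% | 21% v 35% | 14 (17.2) | 1.59 | 35.7 | 20 (22.2) | 1.76 |
| 50% | 15% v 25% | 10 (15.4) | 1.27 | 25.5 | 20 (26.3) | 1.49 |

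The rate ratio is 0.50/0.30 = 1.67 in every row and in both populations.

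**4. What this means for the planned result.** The two tables answer different questions. The mITT table gives the proportion of enrolled subjects who improved by at least k points while meeting the other two criteria. A subject at baseline 6 belongs in that denominator and is correctly outside the numerator for k = 7. Since f is a baseline quantity, randomisation balances it across arms on average, so there is no systematic bias. Section 3.6.5.2 provides only frequencies and proportions for categorical secondary endpoints, so there is no test to lose power.

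**The case for a change.** The strongest argument for acting is that the protocol itself fixes the denominator, in section 3.6.5.2, and does not simply leave it open. Elsewhere it does write a baseline condition into an endpoint: the steroid-reduction endpoint in section 3.6.5 counts only subjects above 7.5 mg/day at baseline. The optional subgroup analyses in that section concern the primary endpoint, so they would not fill the gap. A supportive table would cost little, because the baseline score is already collected.

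What stands is the reachability arithmetic, the absence of any baseline-score condition, and the fact that the strict-cut-off table alone does not separate low opportunity from low effect. Three things keep this from being a fault.

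- **Other planned summaries carry much of the missing information.** Section 3.6.5 plans the 4-point SRI and mSRI, and change from baseline in both indices over time. Even a subject with mSLEDAI-2K 4 can meet mSRI at 4 points. Section 3.6.4 plans descriptive baseline summaries by treatment, though it does not name SLEDAI-2K.
- **Restriction does not resolve the ambiguity.** A subject at baseline 7 would count as able to meet SRI-7, but only by clearing every item to 0. Near-floor subjects remain, and each cut-off and index would have its own baseline-selected subset, not comparable with the others.
- **Nothing prevents the extra table.** A supportive denominator for a descriptive secondary endpoint is the kind of detail section 3.6.2 assigns to the SAP.

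**Conclusion.** The concern does not hold. Some enrolled subjects cannot reach the stricter cut-offs, but the protocol states nothing wrong in counting them. The mITT rates are correct for the population they describe, the arms are affected alike on average, the rate ratio is unchanged, and the endpoints are secondary, descriptive and untested. The primary analysis of mBICLA by MCP-Mod does not use SRI-5 to SRI-8.

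Under the assumed shares of 10%, 30% and 50%, the mITT difference is 2, 6 or 10 points smaller than the 20 points among subjects able to respond. A restricted denominator would raise difference/SE only from 1.93, 1.59 and 1.27 to 2.00, 1.76 and 1.49, and would widen the interval for the absolute difference by 1.3, 5.0 or 10.9 points of half-width. These sizes rest on the assumed shares, response rates and 51 observed subjects per arm; the actual share cannot be derived from the protocol. The conclusion does not rest on them, because at any share the planned table remains valid for the mITT population. A further table among subjects with a sufficient baseline score would be a reasonable preference, but it corrects nothing.
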